## 16.2 Pharmacokinetic Summaries

### 16.2.1 Pharmacokinetic Concentrations

Plasma concentrations for balovaptan, M2, M3 and rifampicin below the quantifiable limit (BQL) will be set to ½ lower limit of quantification (LLOQ) in the computation of mean concentration values.

Descriptive statistics (number of subjects, arithmetic mean, geometric mean, SD, coefficient of variation, median, min, and max) will be used to summarize the serum concentrations by treatment at each scheduled time point. If over ½ the subjects in a given cell have values BQL then the descriptive statistics will not be presented and will instead display as BQL for the mean and minimum. With the exception of maximum all other statistics will be missing.

Linear and semi-logarithmic plots of the geometric mean plasma concentration by scheduled sampling time will be provided by treatment. These plots will show time in hours. The plots will match the summary table results and will not have an observation at a given time point if more than half of the subjects have values BQL.

Linear and semi-logarithmic plots of the individual plasma concentration by actual sampling time will be provided by subject (one subject per page). These plots will show time in hours. Separate plots will be created for the total profile including all analysis periods/treatments and for the Analysis Day 10 time-profiles (balovaptan versus balovaptan + rifampicin) separately. Individual plots will use the BQL handling procedure described below for “Pharmacokinetic Parameters”.

Individual plasma concentration data will be presented together with descriptive statistics by analyte and treatment.

### 16.2.2 Pharmacokinetic Parameters

PK parameters for balovaptan, M2, M3 and rifampicin will be estimated using non-compartmental methods with WinNonlin®.

The plasma PK parameters will be estimated from the concentration-time profiles. In estimating the PK parameters, BQL values will be set to zero for the pre-dose PK sample, as well as for all other samples being BLQ and occurring before  $t_{max}$ . For subsequent time points, the result will be set to missing. Actual sampling times, rather than scheduled sampling times, will be used in all computations involving sampling times. If the actual time or dose time is missing, the scheduled time may be substituted in order to calculate the PK parameter.

Descriptive statistics (number of subjects, arithmetic mean, geometric mean, SD, geometric and arithmetic CV, median, min, and max) will be used to summarize the calculated PK parameters by treatment. For  $t_{max}$ , only median, min and max will be presented.

The points to be included in the  $\lambda z$  range will be determined by the pharmacokineticist after inspection of the semi-log concentration-time profiles. At least 3 points will be required to be used and the range should ideally be spread over a time interval representing at least 2 half-lives. The  $C_{max}$  data point will not be included.

Parameters based on  $R^2$  below 0.70 or %AUCextra above 20% will be flagged and excluded from descriptive statistics.

#### 16.2.2.1 Drug-Drug Interaction

The effect of rifampicin on the PK of balovaptan will be assessed. The effect of rifampicin on the natural log-transformed  $C_{max}$  and AUC0-24h will be assessed with a linear mixed effects model. Treatment will be fitted as fixed effect and subject as a random effect. Point estimates for the means and point estimates and corresponding 90% CI for the differences in means between the two treatments (balovaptan plus rifampicin as the test treatment, versus balovaptan alone as the reference) will be obtained from the linear mixed effects model and exponentiated to obtain geometric means, geometric mean ratios and respective 90% CI on the original scale.

In addition, as an exploratory analysis CYP3A4 genotype will be added as a factor. The relationship between other genotypes (e.g. CYP3A5) may also be explored.

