#### 5.2 Secondary Objectives

- To evaluate the safety and tolerability of balovaptan 10 mg qd administered alone and in combination with rifampicin in healthy subjects.
- To investigate the effect of multiple doses of rifampicin on secondary PK parameters of multiple doses of balovaptan 10 mg qd and its major metabolites M2 and M3 at steady state in healthy subjects.

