##### 5.2.1 Secondary Endpoints

Safety and tolerability:

- Adverse events (AEs)
- Clinical laboratory values

- Vital signs
- Electrocardiogram (ECG)
- Columbia-Suicide Severity Scale (C-SSRS)
- Physical examination

Secondary PK parameters for balovaptan and metabolite M2 and M3:

- Time to maximum observed plasma concentration ( $t_{max}$ )
- Metabolite to parent ratio
- Any other parameter as appropriate (see Table 1)

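### The effect of rifampicin on the metabolite-to-parent ratios is a secondary objective, but no planned analysis reports a within-subject effect estimate with a confidence interval for it

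*SAP*

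**What the plan says.** **Objective.** SAP 5.2 sets the secondary PK objective: "To investigate the effect of multiple doses of rifampicin on secondary PK parameters of multiple doses of balovaptan 10 mg qd", and extends it to M2 and M3. SAP 5.2.1 names two endpoints, "Time to maximum observed plasma concentration" and "Metabolite to parent ratio", and leaves room for others. Table 1 of the protocol (section 2) has the same objective and endpoints. Table 1 of the SAP defines the ratios as MR_Cmax and MR_AUC0-24h for M2 and M3, corrected for molecular weight.

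**Analysis.** SAP 16.2.2 says that descriptive statistics "will be used to summarize the calculated PK parameters by treatment"; for tmax, "only median, min and max will be presented". SAP 16.2.2.1 contains the only between-treatment analysis: "The effect of rifampicin on the natural log-transformed $C_{max}$ and AUC 0-24h will be assessed with a linear mixed effects model", with treatment fixed, subject random and a 90% CI. Protocol 6.6 likewise restricts the model to the primary PK parameters.

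**Outputs.** In SAP Appendix 4, Tables 14.2.2 and 14.2.4 give individual values and descriptive statistics for the parent and metabolite parameters. Table 14.2.7 is the only inferential PK table, and its title refers to balovaptan.

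**The concern.** An effect of rifampicin is a contrast between balovaptan plus rifampicin and balovaptan alone. Each subject receives both, so the natural estimate is the within-subject change. For the metabolite ratios the plan places two summaries side by side and stops there.

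The ratios matter in this study. Protocol 1.2 says that balovaptan, M2 and M3 are all mainly cleared through CYP3A4. Protocol 1.3 expects parent exposure to fall, allows that exposure to some metabolites may rise, and relies on M2's own CYP3A4 clearance when it judges the M2 risk low. The change in the ratio describes that balance directly. If its interval is not prespecified, the report either comments on two geometric means without stating their precision or adds a contrast that SAP 3.0 would require to be identified as unplanned.

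**Working it through.** **1. The plan's own precision figure.** Inputs from SAP 6.1 and protocol 6.1: n = 12, within-subject CV 39% for balovaptan AUC0-24h, 90% CI.

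- Log-scale SD: s = sqrt(ln(1 + 0.39²)) = sqrt(0.1416) = 0.376.
- CI factor = exp(q × s × sqrt(2/n)), with sqrt(2/12) = 0.408.
- q from t on 22 df: factor 1.302. With z and the SD taken as 0.39: 1.299. Both match the stated 1.30.
- q from t on 11 df, the paired analysis: factor 1.318.

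This figure concerns balovaptan exposure. Neither document states a precision for any secondary parameter.

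**2. What the planned outputs already give.** Write M and P for metabolite and parent, T for the combination and R for balovaptan alone. With complete pairs, the mean within-subject change in log(M/P) is

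[mean log(M/P) under T] − [mean log(M/P) under R] = [mean log M_T − mean log M_R] − [mean log P_T − mean log P_R].

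So the ratio of the two tabulated geometric means of MR equals the paired point estimate. It also equals the metabolite geometric mean ratio divided by the parent one, and the molecular-weight correction cancels. This last route needs the model to be run for M2 and M3. Protocol 6.6 includes them, but SAP 16.2.2.1 opens with balovaptan only.

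**3. What the summaries do not give.** The variance of that change depends on the within-subject correlation r between log M and log P, which no summary table reports. For illustration, assume that the metabolite has the same 39% CV as the parent. The SD of the log ratio is then s × sqrt(2(1 − r)), and with n = 12 and t on 11 df the 90% CI factor is:

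| r | factor |
|---|---|
| 0 | 1.48 |
| 0.5 | 1.32 |
| 0.9 | 1.13 |

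The separate geometric mean ratios and their intervals therefore do not fix the interval for the ratio. The individual values do: each subject's MR under each treatment gives the paired log differences directly.

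**4. Precision if the model were fitted to the ratios.** The documents give no within-subject CV for MR, so a range is assumed. Factor = exp(t × s × sqrt(2/n)), with t on n − 1 df:

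| assumed CV of MR | n = 12 | n = 16 |
|---|---|---|
| 10% | 1.08 | 1.06 |
| 20% | 1.16 | 1.13 |
| 30% | 1.24 | 1.20 |
| 39% | 1.32 | 1.26 |
| 50% | 1.41 | 1.34 |

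**5. tmax.** A signed-rank interval for the paired median difference has exact coverage of 90.8% at n = 12, ignoring ties. Ties are likely: protocol 1.2.1.1 puts multiple-dose tmax at 3 to 4 hours, where the sampling times are 2, 2.5, 3, 4 and 6 hours.

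**The case against.** The strongest reply is that nothing is lost. Individual ratios for each treatment will be tabulated, protocol 6.6 also requires individual listings of all PK parameters, and the parameter dataset goes to the sponsor. With at most 16 planned subjects, anyone can compute the paired change and its 90% CI. The SAP follows the protocol in modelling only the primary parameters, the study is exploratory with no hypothesis tests, and neither document promises an interval for a secondary parameter. All of this is correct, and it limits the point to a missing planned analysis. It does not remove the gap between an objective worded as an effect and an analysis with no contrast; that gap is in both documents.

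Two stronger readings are tempting and unsupported. A reader might infer that the study will yield no effect estimate for the ratios, or that an interval is beyond recovery. Steps 2 and 3 show otherwise: the point estimate follows from the geometric means when pairs are complete, and the interval from the individual values.

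A reader might also measure the loss by comparing a paired factor of 1.32 with 1.46 to 1.60 from treating the two summaries as independent samples (between-subject CV of 40% to 60%). The arithmetic is right, but the SAP plans no such independent-samples interval, the between-subject CV has no source in the documents, and 39% is the CV of balovaptan AUC0-24h, not of a ratio.

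On tmax the reply largely succeeds. Median and range with individual values are a reasonable treatment on this sampling grid.

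**Conclusion.** The point stands as a mismatch between objective and analysis for the metabolite-to-parent ratios. No planned output reports a within-subject effect estimate with a confidence interval for MR_Cmax or MR_AUC0-24h, although the design supports one. The consequence is moderate: the primary analysis is unaffected, no data are lost, and a reader could do the calculation. What is missing is a prespecified, reported estimate with its precision.

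The factor of 1.08 to 1.41 rests on an assumed CV of 10% to 50% for the ratio, 12 complete pairs and approximate normality of the log ratio. It shows that an interval is feasible, and is not a forecast of its width. Because the design has one sequence, such an interval would carry any period effect, as the primary intervals do.

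**What to change.** In SAP 16.2.2.1, fit the same mixed model (treatment fixed, subject random) to log MR_Cmax and log MR_AUC0-24h for M2 and for M3. Report the geometric mean ratio of balovaptan plus rifampicin to balovaptan alone with its 90% CI, labelled as a secondary estimate without a hypothesis test, and add the output to SAP Appendix 4. Optionally, report a paired median difference for tmax, with a note that ties are likely. If the team prefers not to add the model, the SAP should at least say that this objective will be addressed descriptively only.

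Cost: a few lines of SAP text, four further runs of an existing model (two ratios × two metabolites), one output and, if wanted, one nonparametric summary. No extra samples or subjects are needed.

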## 17.0 Safety Analyses

### 17.1 Safety Variables

The following safety variables will be summarized:

- Adverse Events (AEs)
- Vital Signs
  - Supine Blood Pressure
    - Systolic Blood Pressure (SBP)
    - Diastolic Blood Pressure (DBP)
  - Pulse rate
  - Body temperature (tympanic)
  - Respiratory rate
- Electrocardiograms (ECG)
  - Heart Rate
  - PR Interval
  - QRS-Duration
  - QT Interval
  - QTc (Fridericia) Interval
- Clinical Laboratory Evaluations
  - Serum Chemistry
  - Hematology
  - Urinalysis
  - Coagulation
- Columbia-Suicide Severity Rating Scale (C-SSRS)
  - Suicidal ideation
  - Suicidal behavior

#### 17.1.1 Adverse Events

All AEs will be coded to the current version of Medical Dictionary for Regulatory Activities (MedDRA, the latest version) by F. Hoffmann-La Roche, Ltd.

All AE summaries will include only treatment emergent adverse events (TEAEs). Treatment-emergent adverse events are those which occur after the first dose of study drug. AEs starting prior to medication dosing in the first period will be regarded as pre-dose AEs (i.e. non-TEAEs).

TEAEs occurring following dosing in a specific analysis period but before dosing in the next analysis period will be attributed to that specific analysis period, thus to the last received treatment. If the time is missing for an AE on a dosing day then the AE will be attributed to the treatment given on that day.

All adverse events (including non-TEAEs) recorded on the eCRF will be listed (including analysis period and treatment information). Pre-dose AEs will be presented in a separate listing. In addition, a separate listing of AEs leading to withdrawal from study will be provided.

TEAEs will be tabulated by system organ class and preferred term: one table with all TEAEs (number and percentage of subjects) overall and by treatment; one table with related TEAEs (number and percentage of subjects) by treatment; one table with all TEAEs (number and percentage of subjects) by treatment and relationship to study drug; one table with TEAEs (number and percentage of subjects) by treatment and severity.

Subjects are counted once, per preferred term per treatment, for the most severe of multiple occurrences (in case of severity) or most drug-related event (in case of relationship) of a specific MedDRA term. AEs

whose causal relationship was characterized as 'Yes'/'No' will be regarded as being related/not related to the study medication.

The following missing data will be imputed as defined (for calculations only / will not be presented):

- Missing AE start and / or end times for the calculation of onset and duration will be assumed to be at 00:01 for a start time and 23:59 for end times
- Missing AE severity or relationship will be assumed to be severe or related, respectively
- Missing AE start times for the determination of treatment emergence will be assumed to occur after treatment unless partial date documents the AE as happening prior to treatment
- Missing AE start times for the determination of treatment assignment will be assumed to occur after treatment on the recorded date one minute after dosing
- Missing AE start date will be attributed to the treatment from analysis period 1 unless the AE end date occurs before first IMP administration

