5.3.5.3 Persistent or Recurrent Adverse Events

A persistent AE is one that extends continuously, without resolution, between subject evaluation timepoints. Such events should only be recorded once on the Adverse Event eCRF (and Form, if appropriate). The initial severity (intensity or grade) of the event will be recorded at the time the event is first reported. If a persistent AE becomes more severe, the most extreme severity should also be recorded on the Adverse Event eCRF (and Form, if appropriate). If the event becomes serious, it should be reported to the Sponsor immediately (i.e., no more than 24 hours after learning that the event became serious; see Section 5.4.2 for reporting instructions). If a nonserious AE becomes serious, the Investigator will complete the paper Clinical Trial Serious Adverse Event/Adverse Event of Special Interest Reporting Form and send the form to Roche drug safety. The Adverse Event eCRF if already completed should also be updated to serious to correspond with the Adverse Event Reporting Form information sent to drug safety.

A recurrent AE is one that resolves between subject evaluation timepoints and subsequently recurs. Each recurrence of an AE should be recorded as a separate event on the Adverse Event eCRF (and Form if appropriate).

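### An adverse event that starts on rifampicin alone and worsens, without resolving, after balovaptan is added is not counted under the combination in any TEAE table

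*SAP*

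**What the plan says.** **Recording (Protocol 5.3.5.3).** An AE that continues without resolution between evaluations gets one record. Two severities can be attached to it. The first is fixed at the outset: "The initial severity (intensity or grade) of the event will be recorded at the time the event is first reported". The second is added later: "If a persistent AE becomes more severe, the most extreme severity should also be recorded on the Adverse Event eCRF". A new record is opened only when an event has resolved and then comes back.

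**Attribution (SAP 17.1.1).** Treatment emergence is set against the start of the study as a whole: "Treatment-emergent adverse events are those which occur after the first dose of study drug". Attribution to a treatment is a separate step: "TEAEs occurring following dosing in a specific analysis period but before dosing in the next analysis period will be attributed to that specific analysis period". The imputation list in the same section shows which variable drives that step, because the rule there is for "Missing AE start times for the determination of treatment assignment". A missing start date is likewise resolved to an analysis period.

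**Counting (SAP 17.1.1).** "Subjects are counted once, per preferred term per treatment, for the most severe of multiple occurrences (in case of severity"; the sentence then gives the parallel rule for relationship.

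**Periods (SAP 9.2.2).** Study Period 2 is split into Analysis Period 2 (rifampicin alone, to Day 6) and Analysis Period 3 (the combination, Days 7 to 16). Rifampicin continues across the boundary and there is no washout.

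**The concern.** One secondary objective is the safety and tolerability of balovaptan alone and in combination with rifampicin (SAP 5.2). A reader will look to the combination column of the TEAE tables for it. If an event is tied to the treatment at its start and has only one record, whatever happens to it after Day 7 has no route into that column.

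Events can plausibly cross the boundary. Protocol 3.3.2.2 names headache, dizziness, nausea, vomiting and raised liver enzymes among the common AEs of rifampicin, and the subject stays on rifampicin when balovaptan is added. Protocol 1.3 gives headache as the most frequent AE with balovaptan in healthy subjects. An event that begins in the six days on rifampicin alone and becomes worse in the ten days on both drugs is relevant to the combination's tolerability, whatever its cause.

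**Working it through.** The plan states no figure on this point, so the check is to apply the written rules to one case.

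**Inputs**
- One record per persistent AE, with initial and most extreme severity: Protocol 5.3.5.3.
- Attribution to a single analysis period, by start: SAP 17.1.1.
- Days up to 6 of Study Period 2 are rifampicin alone, and Days 7 to 16 the combination: SAP 9.2.2.
- Percentages use subjects exposed within a treatment: SAP 9.1.3.
- 16 subjects enrolled to give 12 evaluable: SAP 6.0.

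**Case.** A hypothetical AE starts on Day 5 of Study Period 2 as mild, becomes severe on Day 8, and does not resolve in between.

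1. *Records.* The event is persistent, so there is one record: start Day 5, initial severity mild, most extreme severity severe.
2. *Treatment emergent?* Yes. It starts after the first dose of the study. The definition of a TEAE is not what causes the difficulty.
3. *Attribution.* Day 5 lies in Analysis Period 2, so the event goes to rifampicin alone. No sentence in the SAP splits, moves or recounts it when it worsens on Day 8.
4. *Severity shown.* The SAP does not say which recorded severity feeds the table, so both are worked.

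| Severity used | Rifampicin alone | Combination |
|---|---|---|
| Most extreme | 1 subject, severe | 0 |
| Initial | 1 subject, mild | 0 |
| With the change proposed under the fix | 1 subject, mild | 1 subject, severe |

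The combination entry is zero under either reading of the current text. The same holds in the tables of all TEAEs, of related TEAEs and of TEAEs by relationship, since all of them use the same attribution. If the initial severity is used, the change from mild to severe is in no summary table.

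**Weight of one subject.** 1/16 = 6.25% of a column with all 16 enrolled subjects; 1/12 = 8.33% if only 12 were exposed. Twelve is the evaluable target and not a planned safety denominator, so the second figure is only an illustration of a smaller column.

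**Boundaries of the effect**
- An event that resolves and recurs on or after Day 7 is a new record and is counted under the combination at its own severity.
- An event carried from Study Period 1 into Study Period 2 would meet the same rule, but the 14- to 21-day washout makes that less likely.

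**The case against.** Attribution by onset is a recognised convention, and the plan keeps much of the information elsewhere. All AEs are listed with analysis period and treatment, and SAEs and AEs leading to withdrawal have their own listings. Causality is judged separately for each drug (Protocol 5.3.4). Laboratory, vital-sign and ECG values are summarised by treatment and scheduled time (SAP 17.1.3 to 17.1.5), so worsening in those measurements would show. With 16 subjects the listings can be read line by line. All of this stands and limits the consequence. It does not fill the gap for symptoms, which have no summary by scheduled time, and the listing labels the event with its onset treatment.

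Four stronger inferences are tempting, and the documents do not support them.

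- *The event will be reported as severe under rifampicin alone.* This is the natural reading, because the only selection rule is worst case. But that rule speaks of several occurrences, not of two severities within one event, and both severities are recorded. The SAP leaves it open.
- *The SAP departs from the protocol's definition of an AE, which includes exacerbation.* The exacerbation item in Protocol 5.2.1 refers to 5.3.5.8, which covers conditions present at screening. If such a condition worsens after the first dose, it is a new AE and a TEAE under the SAP. For AEs that arise on study, the SAP follows the protocol's single-record rule.
- *The combination caused the worsening.* Rifampicin continues to Day 16, so longer exposure to rifampicin alone could explain a change on Day 8.
- *The tables will be wrong by 6 to 8 percentage points.* That is the weight of one hypothetical subject. Headache, the obvious example, is often intermittent, and a headache that clears and returns on the combination is counted there.

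**Conclusion.** The point holds in a narrow form. For an AE that begins on rifampicin alone and worsens without a break after Day 7 of Period 2, the written rules leave the combination column empty in every TEAE table. Whether the worsening then appears under rifampicin alone or in no summary table depends on a choice of severity that the SAP does not state.

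The size is one subject per event (6.25 points in a column of 16). The number of such events cannot be estimated from the documents and may be zero. Where it occurs, the effect on the combination column is always an under-count.

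The conclusion assumes that an event occurs in the period in which it starts, which is how the SAP's imputation rules treat it, and that sites follow the single-record rule. It concerns descriptive tables for a secondary objective. The primary PK analysis does not depend on it. The change is a cheap improvement rather than a correction on which the study's conclusions rest.

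**What to change.** Add to the attribution paragraph of SAP 17.1.1, in words such as these: an AE that is ongoing at the start of an analysis period and becomes more severe within that period is also counted as treatment-emergent in that period, at the worse severity; the onset period keeps the severity reached before the change of treatment. This also settles which severity each column shows. The overall column should still count the subject once.

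The rule needs the date on which severity increased. The eCRF is not among the documents, so it may already hold that date, given that both severities are recorded. If it does not, add the date to the AE page.

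The cost is one or two sentences in the SAP and, at most, a small eCRF update. The downside is that one event may be counted under two treatments. A table footnote should say so, and say that the second count does not imply that the combination caused the worsening.

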## 6.0 Study Design

This study will be a single-center, non-randomized, open-label, one-sequence, two-period, within-subject study to investigate the effects of multiple doses of rifampicin on the PK and safety of multiple doses of balovaptan in healthy subjects. The study will be conducted at 1 site in the Netherlands.

Screening will be conducted up to 3 weeks prior to admission in the clinical research unit (CRU). Subjects will be in the CRU for 2 study periods. In both periods, subjects will be admitted on Day -1 (the day before dosing begins); Day 1 will be the first day of dosing. In Period 1, subjects will be discharged on Day 11 after the last assessment is completed. There will be a minimum of a 14-day to a maximum of a 21-day washout between the last dose in Period 1 and the first dose in Period 2. Subjects will therefore return to the CRU on Day 24 or up to Day 30 of Period 1 (Day -1 of Period 2) to begin Period 2. In Period 2, subjects will be discharged on Day 17 after all assessments have been performed. Subjects will return for a follow-up visit between 14 to 21 days after the last dose.

Subjects will receive the following study drugs in the 2 study periods, after an overnight fast of at least 8 hours:

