#### Study Period 1:

[figure not shown]
- Days 1 to 10: oral balovaptan 10 mg qd
- Days 11 to 23 (or up to Day 30): no study drug

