#### Study Period 2:

- Days 1 to 6: rifampicin 600 mg qd
- Days 7 to 16: balovaptan 10 mg qd + rifampicin 600 mg qd

Figure 1 presents an overview of the study design.

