### 9.2.3 Common Variable Derivations

Variable	Data Type	Definition/Calculation	Note
Change from Baseline	All	Post-dose Observation minus Baseline Observation	
Analysis Period	All	Time period starting 1 day before dosing of each of the treatments and ends 1 day before dosing in next analysis period or at the start of the follow-up period for the last treatment.	
Analysis Study Day (Prior to Dose)	All	Date of Measurement minus Dose Date	
Analysis Study Day (Post Dose)	All	Date of Measurement minus Dose Date +1	

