  - b A standardized breakfast will be provided at least 30 minutes after dosing of balovaptan alone, rifampicin alone, or balovaptan + rifampicin together in either period. A standardized lunch and standardized dinner will be provided 4 and 10 hours post dose, respectively, in both periods. Standardized afternoon and evening snacks will be provided as well.
  - c Samples to measure the concentration of balovaptan, M2, and M3 (one sample per time point to measure all 3 analytes) will be taken at predose, and 0.5, 1, 1.5, 2, 2.5, 3, 4, 6, 8, 12, 16, 24, hours post dose on Days 10/11 of Period 1 (16- and 24-hour samples are on the morning of Day 11) and 16/17 of Period 2 (16- and 24-hour samples are on the morning of Day 17). A predose sample to measure the concentration of balovaptan, M2, and M3 will also be taken on Days 2, 4, 8, and 9 in Period 1, and on Days 8, 10, 14, and 15 in Period 2 (see also [Appendix 2](#)).
  - d Samples to measure the concentration of rifampicin will be taken predose and at 1, 1.5, 2, 3, 4, 6, 12, and 24 hours post dose of rifampicin on Days 6/7 and 16/17 of Period 2 (24-hour samples are on the morning of Days 7 and 17) (see also [Appendix 2](#)).
  - e Includes measurement of height, weight and BMI.
  - f Includes measurement of weight.
  - g Triplicate ECGs will be collected as follows: in Period 1, on Day -1 and predose and 3 hours after dosing of balovaptan on Days 3, 7, and 10 and in the morning of Day 11; and in Period 2, on Day -1, and predose and 3 hours post dose on Days 3, 6, 9, 13, and 16; in the morning of Day 17, and at Follow-up (see also [Appendix 2](#)).
  - h Vital signs will be collected as follows: in Period 1, on Day -1 and predose and 3 hours after dosing of balovaptan on Days 3, 7, and 10 and in the morning of Day 11; and in Period 2, on Day -1, and predose and 3 hours post dose on Days 3, 6, 9, 13, and 16; in the morning of Day 17, and at Follow-up (see also [Appendix 2](#)).
  - i Includes measurement of body temperature.
  - j Hematology and chemistry at Screening and on Days -1 and 11 of Period 1 and on Days -1, 3, 6, 9, 13, 17 in Period 2, and follow up. Urinalysis at Screening and on Days -1 and 11 of Period 1 and on Days -1 and 17 in Period 2 and at Follow-up.
  - k For females only: FSH and serum pregnancy test at Screening, and serum pregnancy test only at all other time points.

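### TEAE percentages are tabulated by treatment over unequal observation windows, and the SAP does not settle when the combination window ends

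*SAP*

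**What the plan says.** The attribution rule for adverse events is in SAP 17.1.1: "TEAEs occurring following dosing in a specific analysis period but before dosing in the next analysis period will be attributed to that specific analysis period". It sets no cut-off after the last dose. Tables 14.3.1.1 to 14.3.1.4 report number and percentage of subjects by treatment, and SAP 9.1.3 bases percentages on the subjects exposed to a treatment. SAP 15.0 summarizes how many subjects received each dose. Nowhere does the plan call for subject-days at risk or events per unit of time.

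The schedule in SAP 6.0 is:

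- Balovaptan alone: "Days 1 to 10: oral balovaptan 10 mg qd", then a "minimum of a 14-day to a maximum of a 21-day washout".
- Rifampicin alone: "Days 1 to 6: rifampicin 600 mg qd".
- Combination: "Days 7 to 16: balovaptan 10 mg qd + rifampicin 600 mg qd", with a follow-up visit 14 to 21 days after the last dose.

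The end of the combination window is described in three ways:

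- SAP 9.2.2 gives Analysis Period 3 as Days 7 to 16 of Study Period 2.
- SAP 9.2.3, which applies to all data types, says an analysis period "ends 1 day before dosing in next analysis period or at the start of the follow-up period for the last treatment". It does not define when follow-up starts. The schedule in SAP Appendix 2 places the Follow-up column at Days 30 to 37 of Period 2, while discharge is on Day 17.
- SAP 17.1.1 gives no end, because no dosing period follows. Protocol 5.3.1 collects adverse events until up to 21 days after the last dose.

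**The concern.** A percentage of subjects with at least one event grows with the time over which events are counted. If columns cover different lengths of time, they will differ even when the underlying event rate is the same. The secondary objective is the safety of balovaptan given alone and with rifampicin, and these tables are its main summary. A reader could take a difference created by observation time, or by counting a largely drug-free washout under balovaptan, for a treatment effect. Because the sections conflict and SAP 9.5 provides no table shells, two programmers could also build different tables from the same data.

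**Working it through.** **1. The plan's own figure.** Follow-up falls 14 to 21 days after the last dose on Day 16: 16 + 14 = 30 and 16 + 21 = 37. This reproduces Days 30 to 37 in SAP Appendix 2. The documents state no window length for adverse events and no event rate.

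**2. Windows implied by the text** (first dose of a treatment to first dose of the next, or to the stated end).

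- Balovaptan alone: Day 1 to Day 10 is 9 days, plus 14 to 21 days, giving 23 to 30 days. SAP 6.0 also puts readmission (Day -1) on Day 24 at the earliest, which implies a first Period 2 dose on Day 25 and a lower bound of 24 days. Those dates need reconciling; the effect here is one day.
- Rifampicin alone: Day 1 to Day 7 of Period 2, 6 days.
- Combination to the follow-up visit: 30 − 7 = 23 to 37 − 7 = 30 days.
- Combination under SAP 9.2.2 (Days 7 to 16), or to discharge on Day 17: 10 days.

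**3. Ratios of observation time.**

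| Contrast | Ratio |
|---|---|
| Balovaptan alone vs rifampicin alone | 23/6 = 3.8 to 30/6 = 5.0 |
| Balovaptan alone vs combination, follow-up counted | about 1 (for one subject at most 30/23 = 1.3 either way) |
| Balovaptan alone vs combination, 10-day reading | 23/10 = 2.3 to 30/10 = 3.0 |
| Combination vs rifampicin alone | 10/6 = 1.7, or 3.8 to 5.0 |

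**4. Effect on percentages.** Assume one constant onset rate r per subject-day in every period. Then P(at least one event) = 1 − exp(−r × days).

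| r (assumed) | 6 days | 10 days | 23 days | 30 days |
|---|---|---|---|---|
| 0.01 | 5.8% | 9.5% | 20.5% | 25.9% |
| 0.02 | 11.3% | 18.1% | 36.9% | 45.1% |
| 0.03 | 16.5% | 25.9% | 49.8% | 59.3% |

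With 16 subjects and r = 0.02, that is about 1.8, 2.9 and 5.9 to 7.2 subjects. For rare events the ratio of percentages approaches the ratio of windows, whatever the rate.

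**5. How much of the balovaptan window is off drug.** Protocol 1.2.1.1 gives a half-life of about 46 h after repeated dosing. The washout of 14 × 24 = 336 h to 21 × 24 = 504 h is 7.3 to 11.0 half-lives, so its later part is nearly drug-free.

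**6. Other boundary conflicts.** SAP 9.2.3 starts each analysis period one day before dosing. Day 6 of Period 2, a rifampicin dosing day, then lies in both Analysis Periods 2 and 3, against SAP 9.2.2. An event on Day -1 of Period 2 belongs to Analysis Period 2 under SAP 9.2.2, but to balovaptan alone under 17.1.1.

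**The case against.** The strongest reply is that 17.1.1 is the rule written for adverse events, and under it the contrast named in the objective is fair. The combination has no successor period, events are collected for up to 21 days after the last dose, and so both balovaptan-containing treatments carry a 14 to 21 day tail. That stands. A reader might infer that washout events necessarily inflate balovaptan alone relative to the combination; the documents do not support this. It follows only under the 10-day reading, and the SAP does not say which section governs.

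A reader might also treat rifampicin alone as the planned reference. No objective names that comparison, and SAP 9.2.2 labels only balovaptan alone as reference and the combination as test. The column is nonetheless printed beside the others, with the shortest window throughout.

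Cutting all columns at 24 h after the last dose looks like an easy remedy, but two objections to it hold. It still leaves 10, 6 and 10 days. And at 24 h about 0.5^(24/46) = 70% of the balovaptan level remains, so events under substantial exposure would be labelled as washout. Attribution to the last treatment is a defensible choice for this drug.

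Laboratory monitoring might seem lopsided too ("Hematology and chemistry at Screening and on Days -1 and 11 of Period 1 and on Days -1, 3, 6, 9, 13, 17"). Counted the same way for each treatment under 17.1.1, there are two draws for balovaptan alone (Day 11 and Period 2 Day -1), two for rifampicin alone (Days 3 and 6) and four for the combination (Days 9, 13, 17 and follow-up). Abnormal values become adverse events only on the criteria in Protocol 5.3.5.4. The point does not rest on this.

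Finally, the study is small and descriptive, and SAP 17.1.1 lists every event with its period and treatment, so washout events can be traced by hand. That limits the harm but does not correct the summary tables.

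**Conclusion.** The concern holds in a limited form. Balovaptan alone is observed for 3.8 to 5.0 times as long as rifampicin alone under every reading. The main contrast, balovaptan alone against the combination, is either roughly balanced or 2.3 to 3.0-fold unequal in observation time, and conflicting sections leave open which.

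The window lengths follow from the schedule. The percentages do not: they rest on an assumed rate that is constant across in-house dosing and outpatient washout. If onset is rarer off drug, or less fully reported after discharge, the 37–45% at 2% per day is too high. With 16 subjects, chance variation adds to any such difference. SAP 9.4.3 plans no hypothesis test, so no error rate is affected. The primary pharmacokinetic analysis is untouched.

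**What to change.** 1. Reconcile SAP 9.2.2, 9.2.3 and 17.1.1 into one stated end rule for adverse-event windows, applied identically to balovaptan alone and the combination. Define the start of follow-up, and place Day 6 and Day -1 of Period 2 in one period each.
2. In Tables 14.3.1.1 to 14.3.1.4, keep attribution to the last treatment, but split each balovaptan-containing treatment into on-treatment and post-treatment (washout or follow-up) counts. Pre-specify the cut-off with the 46 h half-life in view. As an illustration, five half-lives is 230 h, or 9.6 days, which gives 9 + 9.6 = 18.6 days on treatment for both and fits inside the shortest washout. The documents give no half-life under rifampicin, so the SAP should say why one cut-off serves both treatments.
3. Print subject-days at risk, or events per subject-day, under every column, with on-treatment and post-treatment time kept apart so that off-drug days do not dilute the on-drug rate. Rifampicin alone is followed directly by the combination and cannot be matched by window, so this is the only way to put it on the same footing.

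The cost is SAP wording, extra table columns and a derived exposure time. No new data and no change in conduct are needed. The small downside is wider tables, with some delayed events appearing in the post-treatment column; none is lost.
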